The investigator is required to evaluate laboratory results related to liver function (AST, ALT, total bilirubin [TBIL], and alkaline phosphatase [ALP]) that could potentially meet criteria for Hy's Law. If these laboratory results include an elevated AST or ALT greater than or equal to $3 \times$ ULN and elevated TBIL greater than or equal to $2 \times$ ULN with an ALP laboratory value that is less than $2 \times$ ULN, the subject will be discontinued from the study and an SAE will be reported. (revised per Amendment 02)

[figure not shown]
In addition, an assessment of suicidal ideation and behavior using the C-SSRS will be performed throughout the study for subjects aged 8 years and older at the time of consent/assent; subjects who will reach the age of 8 years during the double-blind phase of the study will also be assessed using the C-SSRS starting at Baseline. (revised per Amendment 03) Suicidal ideation and behavior will be monitored throughout the study for subjects less than 8 years at the time of consent/assent and during the study, based upon clinical impression. (revised per Amendments 01 and 03). Subjects who appear to have a high risk of suicidal behavior according to results from the C-SSRS and/or clinical impression will be withdrawn from the study. (revised per Amendment 02)

CCI

Safety Assessments – Extension B (revised per Amendment 04)

Safety assessments will consist of monitoring of AEs, withdrawal from treatment, clinical laboratory tests, vital signs, and weight. Concomitant medication usage will be monitored.

CCI

Bioanalytical Method

Plasma concentrations of perampanel will be analyzed using a validated liquid chromatography coupled with tandem mass spectrometry (LC-MS/MS) assay method.

Statistical Methods

Study Endpoints

Primary Endpoints

The primary efficacy endpoint will be the median percent change in drop seizure frequency per 28 days during double-blind treatment (Titration Period and Maintenance Period) relative to the Prerandomization Phase in the Full Analysis Set (FAS)

Secondary Endpoints

[figure not shown]
The following key secondary endpoints will be evaluated sequentially using the FAS:

1. Median percent change in total seizure frequency per 28 days during double-blind treatment (Titration Period and Maintenance Period) relative to the Prerandomization Phase
2. The 50% responder rate in the Maintenance Period of the double-blind treatment relative to the Prerandomization Phase for drop seizures

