9.3.3 Removal of Subjects from Therapy or Assessment

The investigator may withdraw the subject from the study at any time for safety or administrative reasons. The subject may stop study drug or withdraw from the study at any time for any reason.

Subjects with laboratory results that include elevated AST or ALT greater than or equal to $3 \times$ ULN and elevated total bilirubin (TBIL) greater than or equal to $2 \times$ ULN with an alkaline phosphatase (ALP) laboratory value that is less than $2 \times$ ULN, ie that meet criteria for Hy's law, will be withdrawn from the study. (revised per Amendment 03) Subjects who appear to have a high risk of suicidal behavior according to results of the C-SSRS and/or clinical impression will be withdrawn from the study. (revised per Amendment 03)

A subject who discontinues study treatment should be followed for subsequent protocol-specified visits and procedures. If a subject discontinues study drug(s) but remains in the study (Core Study), the set of end-of-treatment procedures will be administered, and protocol-specified information will be collected. The primary reason for discontinuation and all other reason(s) contributing to the subject's discontinuation from study drug(s) should be collected on the Subject Disposition case report form (CRF) page (or the Early Discontinuation from Study Drug CRF page). In addition, the date of last dose of study drug(s) will be recorded on the Study Drug Dosing CRF page. If a subject discontinues study treatment and the study at the same time, the End-of-Study procedures (Final Visit) will be followed.

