9.5.1.5 Safety Assessments

Safety assessments will consist of monitoring and recording all AEs and SAEs; regular laboratory evaluation for hematology, blood chemistry, including assessment of criteria for Hy's Law and urine values; and periodic measurement of vital signs as detailed in [Table 5](#). Reports of

anxiety and irritability will be closely monitored during the study by both the investigators and the Medical Monitor. (revised per Amendment 01)

The investigator at each site is required to evaluate laboratory results related to liver function (AST, ALT, TBIL, andALP), as determined by way of protocol-specified laboratory testing or unscheduled laboratory testing. If these laboratory results include elevated AST or ALT greater than or equal to $3 \times$ ULN and elevated TBIL greater than or equal to $2 \times$ ULN with an ALPlaboratory value that is less than $2 \times$ ULN, the subject will be discontinued from the study. Any laboratory results that are more than 3 times greater than the ULN for ALT or AST will be flagged by the central laboratory for investigator review. These laboratory abnormalities should be reported as an SAE. (revised per Amendment 02)

Please note that besides the laboratory abnormalities noted above, the criteria for Hy's Law include the stipulation that no other reason can be found to explain the combination of increased ALT, AST and TBL, such as viral hepatitis A, B, or C; preexisting or acute liver disease; or another drug capable of causing the observed injury. The investigator should document causality. (revised per Amendment 02)In addition, assessments of suicidal ideation and behavior using the C-SSRS will be performed during the study for subjects aged 8 years and older at the time of consent/assent; subjects who will reach the age of 8 years during the double-blind phase of the study will also be assessed using the C-SSRS starting at Baseline. (revised per Amendment 03) Suicidal ideation and behavior will be monitored in subjects less than 8 years at the time of consent/assent and during the study, on the basis of clinical impression. (revised per Amendments 01 and 03) Subjects who appear to have a high risk of suicidal behavior according to results from the C-SSRS and/or clinical impression will be withdrawn from the study. (revised per Amendment 03)

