- Is life-threatening (ie, the subject was at immediate risk of death from the adverse event as it occurred; this does not include an event that, had it occurred in a more severe form or was allowed to continue, might have caused death)
- Requires inpatient hospitalization or prolongation of existing hospitalization
- Results in persistent or significant disability/incapacity
- Is a congenital anomaly/birth defect (in the child of a subject who was exposed to the study drug)

Other important medical events that may not be immediately life-threatening or result in death or hospitalization but, when based on appropriate medical judgment, may jeopardize the subject or may require intervention to prevent one of the outcomes in the definition of SAE listed above

should also be considered SAEs. Medical and scientific judgment should be exercised in deciding whether expedited reporting is appropriate in such situations.

For this study, the following events should always be considered serious and reported as an important medical event if they do not meet other serious criteria: status epilepticus, laboratory results of elevated AST or ALT greater than or equal to $3 \times$ ULN and elevated TBIL greater than or equal to $2 \times$ ULN with an ALP laboratory value that is less than $2 \times$ ULN, and reports of aggression when the aggressive act resulted in another person requiring medical treatment or the aggressive act or threat involved a weapon. (revised per Amendment 02)

In addition to the above, events associated with special situations include pregnancy or exposure to study drug through breastfeeding; AEs associated with study drug overdose, misuse, abuse, or medication error. (revised per Amendment 02) These events associated with special situations are to be captured using the SAE procedures but are to be considered as SAEs only if they meet one of the above criteria. All AEs associated with special situations are to be reported on the CRF whether or not they meet the criteria for SAEs.

The following hospitalizations are not considered to be SAEs because there is no “adverse event” (ie, there is no untoward medical occurrence) associated with the hospitalization:

- Hospitalizations for respite care
- Planned hospitalizations required by the protocol
- Hospitalization planned before informed consent (where the condition requiring the hospitalization has not changed post study drug administration)

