9.5.4.3 Reporting of Events Associated with Special Situations

REPORTING OF ADVERSE EVENTS ASSOCIATED WITH STUDY DRUG OVERDOSE, MISUSE, ABUSE, OR MEDICATION ERROR

Adverse events associated with study drug overdose, misuse, abuse, and medication error refer to AEs associated with uses of the study drug outside of that specified by the protocol. Overdose, misuse, abuse, and medication error are defined as follows:

| | |
|------------------|---|
| Overdose | Accidental or intentional use of the study drug in an amount higher than the protocol-defined dose |
| Misuse | Intentional and inappropriate use of study drug not in accordance with the protocol |
| Abuse | Sporadic or persistent intentional excessive use of study drug accompanied by harmful physical or psychological effects |
| Medication error | Any unintentional event that causes or leads to inappropriate study drug use or subject harm while the study drug is in the control of site personnel or the subject. |

All AEs associated with an overdose should be captured on the Adverse Event CRF. Adverse events associated with overdose, misuse, abuse, or medication error should be reported using the procedures detailed in Reporting of Serious Adverse Events ([Section 9.5.4.1](#)) even if the AEs do not meet serious criteria. Abuse is always to be captured as an AE. If the AE associated with an overdose, misuse, abuse, or medication error does not meet serious criteria, it must still be reported using the SAE form and in an expedited manner, but should be noted as nonserious on the SAE form and the Adverse Event CRF.

REPORTING OF STUDY-SPECIFIC EVENTS

For this study, the following events should always be considered serious and reported as an important medical event even if it does not meet other serious criteria: status epilepticus, laboratory results of elevated AST or ALT greater than or equal to $3 \times \text{ULN}$ and elevated TBIL greater than or equal to $2 \times \text{ULN}$ with an ALP laboratory value that is less than $2 \times \text{ULN}$, and reports of aggression when the aggressive act resulted in another person requiring medical treatment or if the aggressive act or threat involved a weapon. (revised per Amendments 01 and 02)

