Laboratory analyses will also include analysis of outliers. For ALT and AST analysis, the number of subjects with >3 times but <5 times the ULN and the number of subjects with >5 times the ULN will be summarized. For bilirubin, a summary of the number of subjects with serum concentrations >2 times the ULN will be created. The number of subjects who meet the criteria for Hy's Law ([Section 9.5.1.5](#)) will be summarized by visit and during the treatment duration. (revised per Amendment 02) The number of subjects who meet each of the criteria for Hy's Law during treatment (but not all necessarily at the same visit) will also be summarized. (revised per Amendment 01)

VITAL SIGNS

Descriptive statistics for vital signs parameters (ie, diastolic and systolic BP, pulse) and changes from baseline to each visit and to the last visit of the double-blind treatment will be presented by treatment group.

OTHER SAFETY ANALYSES

Pregnancy Test

By-subject listings will be presented for pregnancy tests.

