For alanine amino transferase (ALT), aspartate amino transferase (AST) and alkaline phosphatase, the number of subjects with $> 3x$ but $\leq 5x$ the Upper Limit Normal (ULN) and the number of subjects with $> 5x$ the ULN will be summarized by treatment group by visit. For bilirubin, the number of subjects with serum concentrations $> 2x$ ULN will be summarized by treatment group by visit. These summaries will also be provided for the maximum value in the treatment duration. In addition, the number of subjects who meet the criteria for Hy's Law at the same visit will be summarized by visit and during the treatment duration. A subject will be determined to have met Hy's Law if AST or ALT is $> 3x$ ULN, bilirubin $> 2x$ ULN, and alkaline phosphatase $\leq 2x$ ULN at a visit. The number of subjects who meet each of the criteria for Hy's Law during treatment (but not all necessarily at the same visit) will also be summarized.

Potentially clinically significant (abnormal) changes, defined as an increase in NCI grade to Grade 2 or higher from baseline when the baseline value is normal will be summarized.

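### The SAP's laboratory definition of Hy's Law swaps strict and inclusive limits on all three limbs of the protocol rule it is meant to count; on those thresholds the results can differ only at exact ties

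*SAP*

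**What the plan says.** The protocol sets the rule in several places with the same limits. Section 9.5.1.5 gives the discontinuation rule: "If these laboratory results include elevated AST or ALT greater than or equal to" 3×ULN, together with total bilirubin at or above 2×ULN and ALP below 2×ULN. The list of events always treated as serious, in the same section, repeats it ("ULN with an ALP laboratory value that is less than" 2×ULN), and so does Section 9.5.4.3 ("with an ALP laboratory value that is less than" 2×ULN). Section 9.3.3 makes it a withdrawal rule ("Subjects with laboratory results that include elevated AST or ALT greater than or equal to" 3×ULN, and so on) and states that these results are what meeting Hy's Law means. The Synopsis gives the consequence: "the subject will be discontinued from the study and an SAE will be reported".

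For the analysis, Protocol 9.7.1.8 says what is to be tabulated, with a cross-reference to Section 9.5.1.5: "The number of subjects who meet the criteria for Hy's Law", by visit and over the treatment duration. It adds a second count, of subjects meeting each criterion but not necessarily at one visit.

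SAP 5.6.3 plans both counts but defines the criteria differently: "A subject will be determined to have met Hy's Law if AST or ALT is $> 3x$ ULN, bilirubin $> 2x$ ULN". For the third limb the limit becomes inclusive: "and alkaline phosphatase $\leq 2x$ ULN at a visit". SAP section 7 says that the statistical methods are unchanged from the protocol.

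**The concern.** The protocol does not leave the definition to the SAP; it points to its own section. The SAP makes the two inclusive limits strict and the one strict limit inclusive, without declaring a change. A reader of the Hy's Law table would take it to show subjects who met the protocol rule.

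At a boundary value the table can be wrong in either direction. It can leave out a subject who was withdrawn and reported as an SAE under the rule. It can also show a subject whose ALP was exactly 2×ULN and who did not meet the rule. In both cases the liver-safety table would not reconcile with the disposition and SAE records.

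**Working it through.** The plan gives no figure to reproduce here, so the check compares the two rules.

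**Inputs**

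| Limb | Protocol 9.5.1.5 | SAP 5.6.3 | Value exactly at the limit |
|---|---|---|---|
| AST or ALT | ≥3×ULN | >3×ULN | met under the protocol only |
| Total bilirubin | ≥2×ULN | >2×ULN | met under the protocol only |
| ALP | <2×ULN | ≤2×ULN | met under the SAP only |

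**Same-visit count.** Let T be the larger of AST and ALT, B total bilirubin and P ALP, all in multiples of ULN. Using the larger value is exact, because either enzyme passes a lower limit if and only if the larger one does.

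- Protocol: T ≥ 3 and B ≥ 2 and P < 2.
- SAP: T > 3 and B > 2 and P ≤ 2.

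Each of T, B and P lies below, at or above its limit, which gives 3 × 3 × 3 = 27 patterns.

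- No value at a limit: 2 × 2 × 2 = 8 patterns. The rules agree on all 8.
- At least one tie: 27 − 8 = 19 patterns. The rules disagree on 4:
  - T at, B at, P below: protocol only.
  - T at, B above, P below: protocol only.
  - T above, B at, P below: protocol only.
  - T above, B above, P at: SAP only.
- The other 19 − 4 = 15 tie patterns are not met under either rule.

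Examples, as (T, B, P):

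- (3, 2.5, 1.5) and (4, 2, 1.5) meet the protocol rule but not the SAP rule.
- (4, 2.5, 2) meets the SAP rule but not the protocol rule.
- (4, 2.5, 1.5) meets both.
- (3, 2.5, 2) meets neither.

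These are logical patterns, not frequencies; 4 out of 27 is not an error rate.

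**Count over the treatment duration.** A subject missed because of a tie at one visit is still counted if another visit within the treatment duration meets the SAP rule. For laboratory data, SAP 8.2.2 ends that period 14 days after the last dose.

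**Each-criterion row.** The limbs need not coincide here. If the row is tabulated limb by limb, a tie in one limb changes that limb's count whatever the others show. If it counts subjects who meet all three limbs at some time, the other two must still be met, possibly at other visits.

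**After the change.** With ≥3×, ≥2× and ALP <2×ULN in the SAP, the two laboratory rules are identical and no pattern disagrees.

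**The case against.** **The strict limits have precedents in the protocol.** Section 9.7.1.8 summarises liver outliers at more than 3×ULN for ALT and AST and more than 2×ULN for bilirubin. Section 9.5.1.5 itself has the central laboratory flag ALT or AST above 3×ULN, so a value of exactly 3×ULN would not be flagged. This may explain where two of the SAP's limits came from, and it shows that the protocol is not uniform at the transaminase boundary. It does not alter the ≥3×ULN rule, which is restated for withdrawal and for SAE reporting. Nor does it explain ALP: Section 9.7.1.8 sets no ALP outlier limit, and Appendix 1 grades ALP at 1, 3, 5 and 20×ULN, not 2.

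**Hy's Law needs more than laboratory values.** Section 9.5.1.5 adds that no alternative explanation may be found, and SAP 5.6.3 does not apply this. If the count were read to include that condition, it could differ without any tie. A reader might therefore take the statement that differences need a tie as covering the whole definition; it covers the laboratory thresholds only. Comparing on laboratory values is the natural reading, because Section 9.3.3 equates the laboratory results with Hy's Law and Section 9.7.1.8 places the count among the laboratory outliers. The causality condition is a separate point.

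**It hardly matters in practice.** This stands. The count is descriptive, in about 142 planned subjects, and scheduled laboratory tests after the start of dosing and up to the end of treatment are few (Visit 4, and Visit 7 or early discontinuation). Stable ALT or AST elevations due to concomitant medication are allowed at entry only below 3×ULN.

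**Conclusion.** The SAP definition contradicts the protocol rule it is meant to count on all three limbs, and the departure is undeclared. On the laboratory thresholds alone, the same-visit count differs only at an exact tie with the other limbs met, in either direction. The each-criterion row may differ on a tie in one limb. The documents give neither a tie frequency nor an expected number of Hy's Law cases, so the effect cannot be put as a rate; it should be very small.

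A reader might infer that subjects with possible drug-induced liver injury would escape withdrawal or reporting. The documents do not support that. Those actions follow the protocol rule during the study, and a protocol-defined case reported as an SAE appears in the SAE listing planned in SAP 5.6.2.1. No hypothesis test or power figure is involved. This is an alignment correction worth making because it costs almost nothing.

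**What to change.** In SAP 5.6.3, define the criteria as AST or ALT ≥3×ULN, total bilirubin ≥2×ULN and ALP <2×ULN at the same visit. Use the same three limits for the row that does not require the same visit. Label both rows as laboratory criteria for Hy's Law, so that they are not read as including the causality assessment.

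A subject exactly at 3×ULN or 2×ULN could then appear in the Hy's Law row but not in the matching outlier row, which keeps its strict limit. That difference already exists in the protocol, and a table footnote would cover it.

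The cost is three operators and a row label in the SAP, plus the matching change in the programming specifications. Those are separate documents not available here, so the size of that last step is an assumption. No protocol amendment and no new data are needed.

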5.6.4 Vital Signs

Descriptive statistics for vital signs parameters (diastolic and systolic blood pressure, pulse, respiration rate, temperature, weight, height) and changes from baseline to each post-baseline visit and to the last post-baseline visit will be presented by treatment group

In addition, the criteria described in [Table 1](#) will be used to determine clinically notable results for blood pressure and heart rate. The number (percentage) of subjects with clinically notable results over all scheduled and unscheduled visits will be summarized by treatment group.

Table 1: Criteria for Clinically Notable^a Vital Signs

Variable	Criterion Value	Change Relative to Baseline
Systolic BP	> 180 mmHg	Increase of ≥ 20 mmHg
	< 90 mmHg	Decrease of ≥ 20 mmHg

Diastolic BP	>105 mmHg	Increase of ≥ 15 mmHg
	< 50 mmHg	Decrease of ≥ 15 mmHg
Heart Rate	>120 bpm	Increase of ≥ 15 bpm
	< 50 bpm	Decrease of ≥ 15 bpm
Weight		Increase of $> 7\%$
		Decrease of $> 7\%$
a: Clinically notable means that a value must have met both the criterion value and satisfied the magnitude of change relative to baseline.		

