9.3 SELECTION OF STUDY POPULATION

Approximately 142 subjects will be randomized at approximately 70 sites in regions that include North America, Europe, and Asia. Approximately 30% of subjects will be recruited from the US. Sites will be encouraged to enroll subjects throughout the allowed age range (2 years and older). Subjects who do not meet all of the inclusion criteria or who meet any of the exclusion criteria will not be eligible to receive study drug.

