9.3.1 Inclusion Criteria

Subjects must meet all of the following criteria to be included in this study:

1. Subjects must have diagnosis of LGS as evidenced by:
 - a. More than one type of generalized seizures, including drop seizures (atonic, tonic, or myoclonic) for at least 6 months before Visit 1

- b. An EEG reporting diagnostic criteria for LGS at some point in their history (abnormal background activity accompanied by slow, spike and wave pattern < 2.5 Hz)
2. Subjects must be at least 2 years old at the time of consent/assent
3. Subjects must have been <11 years old at the onset of LGS
4. Subjects must have experienced an average of at least 2 drop seizures per week in the 4-week Baseline Period preceding randomization; the Baseline Period within the Prerandomization Phase is (minimum) 4 weeks. (revised per Amendment 04)
5. Subjects must have been receiving 1 to 4 concomitant AEDs at a stable dose for at least 30 days before Visit 1 (vagal nerve stimulation [VNS] and ketogenic diet do not count as an AED). Use of cannabidiol (CBD) products is allowed and is counted as one of the 4 maximum allowed concomitant AEDs. CBD dose and product must have remained stable for at least 30 days before Visit 1 and is to remain the same throughout the course of the Core Study. (revised per Amendment 04)
6. In the investigator's opinion, parents or caregivers must be able to keep accurate seizure diaries
7. Body weight at least 8 kg

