5.3.4 Examination of Subgroups

The following endpoints will be summarised by age (2-<12, 12-<18, 18-<65, ≥65):

Disposition; demography; epilepsy-specific medical history, number of baseline AEDs, baseline AEDs, compliance, percent change in drop, non-drop and total seizure frequency, 50%/75% response and seizure freedom rates in drop, non-drop and total seizures; clinical global impression exposure; treatment-emergent adverse events; change from baseline in laboratory values; treatment-emergent markedly abnormal laboratory values; change from baseline in vital signs; and Columbia Suicide Severity Rating Scale (C-SSRS), for subjects 8 years and over.

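### One set of absolute vital-sign limits from age 2 upward makes the high-blood-pressure and low-heart-rate flags in SAP 5.6.4 insensitive in young children, and the weight rows cannot be applied as written

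*SAP*

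**What the plan says.** SAP 5.6.4 (core study) first plans descriptive statistics for vital signs and their changes from baseline, by visit and treatment group. It then adds Table 1, whose criteria "will be used to determine clinically notable results for blood pressure and heart rate". (Another table in SAP 8.2.2 is also numbered 1; this point concerns the criteria table in 5.6.4.)

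The limits are:

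| Variable | High flag | Low flag |
|---|---|---|
| Systolic BP | >180 mmHg and rise ≥20 | <90 mmHg and fall ≥20 |
| Diastolic BP | >105 mmHg and rise ≥15 | <50 mmHg and fall ≥15 |
| Heart rate | >120 bpm and rise ≥15 | <50 bpm and fall ≥15 |
| Weight | no limit; rise >7% | no limit; fall >7% |

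Footnote a joins the two columns: "Clinically notable means that a value must have met both the criterion value and satisfied the magnitude of change relative to baseline". The table carries no age column and no age restriction. The planned output is the number and percentage of subjects with a flag; "clinically notable results over all scheduled and unscheduled visits will be summarized by treatment group".

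Protocol 9.3.1 sets the lower age limit, "Subjects must be at least 2 years old at the time of consent/assent", with a minimum weight of 8 kg and no upper age limit. SAP 5.3.4 says "The following endpoints will be summarised by age", using the groups 2-<12, 12-<18, 18-<65 and ≥65. Its vital-sign item is "change from baseline in vital signs". SAP 5.6 adds exposure, treatment-emergent adverse events and markedly abnormal laboratory values by age group. Neither list includes the notable vital-sign flag.

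**The concern.** A limit chosen for adults does different work in a small child. Young children usually have lower blood pressure and faster pulse than adults. That is general knowledge and is not stated in the documents. If it holds, the upper pressure limits and the lower heart-rate limit lie far from where a child starts, and a change that the SAP itself treats as material would not be counted.

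The table has some weight here because SAP 5.6.5 takes ECGs at Screening only and summarises none of them. Table 1 is also the only core analysis that counts individual vital-sign outliers. Elsewhere the SAP does adapt to age: lymphocyte grades are not applied below 12 (SAP 13.1), and dose is expressed per kilogram below 12 (SAP 5.6.1).

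The weight rows raise a separate drafting problem. Weight change is of interest in this programme: the protocol's revision history for version 4.0 gives a regulator's concern about weight gain as a reason for fasting laboratory samples.

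**Working it through.** The plan states no figure to reproduce. The check applies Table 1's two-part rule to whole-number readings.

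**Step 1: the first flagged value from baseline b**

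- High flag: max(limit + 1, b + change criterion).
- Low flag: min(limit − 1, b − change criterion).

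**Step 2: where the absolute limit overrides the change criterion.** This uses Table 1 alone, with no assumption about children.

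- Systolic high: 181 − b > 20, so b ≤ 160.
- Diastolic high: 106 − b > 15, so b ≤ 90.
- Heart rate low: b − 49 > 15, so b ≥ 65.

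Over those baselines the stated change criterion plays no part in the flag.

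**Step 3: the change needed at paediatric baselines.** The documents give no paediatric norms, so these baseline ranges are assumptions.

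| Flag | Assumed baseline | Change needed | SAP's own change criterion |
|---|---|---|---|
| Systolic high | 80 to 110 | 181 − 80 = 101 down to 181 − 110 = 71 mmHg | 20 mmHg |
| Diastolic high | 45 to 75 | 106 − 45 = 61 down to 106 − 75 = 31 mmHg | 15 mmHg |
| Heart rate low | 80 to 130 | 80 − 49 = 31 up to 130 − 49 = 81 bpm | 15 bpm |

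Two examples: a systolic rise of 50 from 95 to 145 mmHg is not flagged, because 145 does not exceed 180. A heart-rate fall of 45 from 100 to 55 bpm is not flagged, because 55 is not below 50.

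**Step 4: the opposite direction.** The change criterion alone decides the flag when:

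- heart rate high: 121 − b ≤ 15, so b ≥ 106;
- systolic low: b − 89 ≤ 20, so b ≤ 109;
- diastolic low: b − 49 ≤ 15, so b ≤ 64.

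These limits are within reach for a child. How often ordinary variation crosses them cannot be worked out, because the documents say nothing about within-child variability.

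**Step 5: weight.** Footnote a needs a criterion value and a change. The weight rows have no criterion value, so read literally the condition can never be met. The lead-in sentence names only blood pressure and heart rate, so it does not settle whether weight belongs in the table.

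**The case against.** The strongest reply is that this is one supplementary descriptive table and the plan has other ways to see a problem.

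- Changes from baseline in vital signs are summarised by age group, including 2-<12, and SAP 5 includes minimum and maximum among the descriptive statistics.
- Adverse events are summarised by age group, and the cardiac adverse-event queries in SAP 5.6.2.2 cover slow and fast arrhythmias.
- An extreme value, such as systolic pressure above 180 with the required rise, is flagged at any age.

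All of this stands. It means insensitive, not unseen. Summary statistics by visit do not, however, count how many children had a material change.

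A reader might infer that the tachycardia and hypotension rows would be swamped by normal paediatric readings. The documents do not support that. With an assumed heart-rate range of 80-120, no reading exceeds 120. With systolic 85-105, the only qualifying pair is 105 falling to 85. Wider ranges allow some flags, but no frequency can be given. Protocol 9.5.1.5 also has pulse and pressure taken after five minutes sitting, which limits readings inflated by distress. Over-flagging is possible but not shown.

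A reader might also infer that the secondary endpoint on vital-sign changes is compromised. It is not: those changes are analysed directly, and no test or significance level uses Table 1.

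On weight, a blank cell may well have been meant as change only. That is a sensible intention, but the footnote says otherwise and the text should be made to agree. It is also tempting to say that a 7% gain would flag normal growth. Seven per cent of the minimum weight of 8 kg is 0.56 kg, but the documents contain no growth rates from which to show how often growth alone would reach that.

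**Conclusion.** The point holds in a narrow form. From Table 1 alone, the absolute limit overrides the SAP's change criterion at every baseline systolic pressure up to 160 mmHg, diastolic up to 90 mmHg, and heart rate from 65 bpm. Under the assumed paediatric baselines, the required change is roughly 3.6 to 5.1 times the SAP's own criterion for systolic pressure (71/20 to 101/20), 2.1 to 4.1 times for diastolic (31/15 to 61/15) and 2.1 to 5.4 times for low heart rate (31/15 to 81/15). The direction is the same across the whole of each range. The table is therefore a poor detector of raised pressure and bradycardia in young children, and because it is not split by age, a reader cannot see this from the output.

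The weight rows are internally inconsistent whatever baselines are assumed.

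The consequence is confined to a descriptive safety summary; the primary analysis, power and error control are untouched. The conclusion rests on the assumed baselines and on the SAP text. The separate programming specifications mentioned in SAP 9 were not available and could contain an age rule, but nothing in the SAP points to one.

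**What to change.** In SAP 5.6.4:

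1. For subjects under 12, replace the absolute limits with age-appropriate reference limits from a named source, fixed before unblinding, and keep the change criterion. Dropping the limits and flagging on change alone is not the better route: a move from 90 to 105 bpm, inside the assumed range, would then be flagged.
2. Report the notable-value table by the four age groups already used in SAP 5.3.4, as well as by treatment group.
3. State that weight is flagged on the >7% change alone, exempt it from footnote a, and name weight in the lead-in sentence. Read the result by age group, because growth contributes in children.

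The cost is choosing and citing a reference table and a little programming. Age, weight, blood pressure and pulse are already collected, so no protocol amendment is needed. If the SAP is already final, its section 7 provides for later changes to be documented separately and addressed in the clinical study report.
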